4.1 Eligibility criteria

Eligibility criteria are described in SEESAW_Protocol_v7.0 20.03.2018.

4.2 Recruitment

A CONSORT chart will display the flow of patients through the trial.

4.3 Baseline characteristics

The demographic and clinical characteristics and medical history will be tabulated and summarised by treatment groups and in total. This will include the stratification variables.

Numbers (with percentages) for binary and categorical variables and medians (with lower and upper quartiles and minimums and maximums) for continuous variables will be presented. There will be no formal comparison of baseline variables between treatment groups.

5 Analysis

5.1 Primary outcome definitions

The primary outcome is change in 3-hour time averaged AUC of PYY from baseline to week 24.

The PYY outcome is based on the response to a standardised mixed breakfast with data collected pre- and postprandially, specifically fasted (pre-standardised breakfast), 30 minutes post-breakfast and then 60 minutes, 90 minutes, 120 minutes, 150 minutes and 180 minutes post-breakfast. PYY AUC will be derived using the trapezium rule and then divided by time period to calculate the time averaged AUC. This represents the average PYY response across the postprandial period.

PYY 3-hour time averaged AUC responses at 2 weeks, 6 weeks, and 12 weeks follow-up will be analysed in the same way as the primary outcome and investigated as secondary outcomes.

5.2 Secondary outcome definitions

Below is a list of all of the secondary outcomes collected at baseline and at least one followup visit. Outcomes measured at 2, 6 and 12 weeks will be treated as secondary outcomes.

(i) Appetite hormones ghrelin and GLP-1 and appetite perception Ghrelin and GLP-1 will each be recorded in the same manner as the primary outcome, i.e. as time averaged AUC.

(ii) Resting energy expenditure

(iii) Change in blood and urine biochemical parameters.

- Insulin time averaged AUC
- Glucose time averaged AUC
- Glucagon time averaged AUC
- C-peptide time averaged AUC

The above biochemical parameters will be measured at 7 time points specifically, fasted (pre-standardised breakfast), 30 minutes post-breakfast and then 60 minutes, 90

minutes, 120 minutes, 150 minutes and 180 minutes post-breakfast. Time averaged AUC values will be calculated as per that for PYY.

- Leptin
- HbA1c
- C-reactive protein
- Fasting plasma glucose
- Lipids (total HDL and LDL cholesterol, FFAs)
- eGFR
- urinary glucose excretion
- ALT
- Leptin

(iv) Physical activity measures:

 ActiGraph for assessment of daily step count and daily time spent sedentary and in light-intensity and moderate-to-vigorous intensity physical activity (including only those people with at least 3 days of data)

(v) Study questionnaires

- Three-Factor Eating Questionnaire this will assess the patient's eating traits (restraint, disinhibition, hunger)
- International Physical Activity Questionnaire (IPAQ) —to assess walking, moderate and vigorous activities, along with time spent sedentary.
- Visual Analogue Scale (VAS) which will measure perceived hunger, fullness, satisfaction and prospective food consumption ratings. VAS is measured at every time point as per the blood samples and so will also be analysed as an AUC measure, as per that for PYY.

(vi) Anthropometric measures:

- Body weight (kg)
- Body fat (%)
- Fat mass (kg)
- Bone mass (kg) and density (g/m²)
- Muscle mass (kg)
- Waist circumference (cm)
- Hip circumference (cm)

(vii) Cardiovascular measures:

- Blood pressure (mmHg)
- Resting heart rate (bpm)

5.3 Analysis methods

5.3.1 Analysis of primary and secondary outcomes

A generalised linear model will be used with PYY 3-hour time averaged AUC at 24 weeks entered as the dependant variable and randomisation group entered as a categorical independent variable with the placebo control group as the reference. The effect of the intervention will be adjusted for baseline value of PYY and stratification variables (Age & BMI grouped as two categories as per the stratification method). Data will be checked for normality with an appropriate distribution (i.e. gamma) or transformation used if time averaged AUC PYY is not normally distributed, although we anticipate data will be normally distributed. The overall p value for the effect of treatment will be reported.

5.3.2 Confidence intervals and p-values

The threshold for a significant treatment effect for each intervention group vs placebo control (3 comparisons) will be determined through post-hoc tests using Holm's Sequential Bonferroni procedure with thresholds set at 0.017 for the most significant comparison, 0.025 for the next most significant comparison and 0.05 for the least significant comparison. Tests for significance will stop once any of these thresholds are met or exceeded. For consistency and to allow for a comparison of variance across groups, data will be reported as the mean adjusted intervention effect (change in the intervention of interest minus change in the comparator; mean, 95% CI). Inferences of significance will not be made based on the 95% CI.

5.3.3 Secondary outcomes

PYY time averaged AUC responses at weeks 2, 6 and 12 will also be analysed using the same methods as above. For summary purposes, Generalised Estimating Equations (GEE) taking account of repeated measures (2, 6, 12 and 24 weeks) with an exchangeable correlation matrix adjusted for baseline value and stratification variables (Age & BMI) will be used to derive an average PYY AUC response across time for each of the intervention groups compared to the control group, with significance assigned using the same method as that described for the primary outcome. Objective physical activity measures will be adjusted for ActiGraph wear time at baseline and follow up.

All other secondary outcomes will be analysed using the same approach as that described for the primary outcome. Models of ActiGraph measured outcomes will additionally be adjusted for ActiGraph wear time at baseline and follow-up.

5.4 Missing data

5.4.1 Missing data for AUC values – complete case analysis

This study includes AUC values as the primary and key secondary outcomes, with AUC values calculated using data collected over 7 time points; fasting (pre-standardised

breakfast), and at 30 minutes post-breakfast and then 60 minutes, 90 minutes, 120 minutes, 150 minutes and 180 minutes post-breakfast. Those with at least 4 valid values across the sampling time points will be included in the complete case analysis. Those with 4 or more missing data points will be excluded from the complete case analysis.

Those with at least 4 valid data points will have missing time point data using a regression method. Specifically, for each time-point a regression model will be fitted that includes BMI, age, ethnicity, randomisation group, and fasting PYY (excluded from the regression model for fasting PYY). Fitted estimates of PYY will be produced for each participant at each time-point based on the relevant regression model, and used to impute missing data.

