2.3 Sample size

The power calculation is based on the primary outcome of total PYY with a standard deviation of area under the curve (AUC) of 96.2pg/ml, based on a study looking at the influence of resistance and aerobic exercise on hunger and circulating levels of total PYY in healthy males³. To detect a minimum clinically significant difference of 120pg/ml in AUC of total PYY between groups, we will require 15 patients (60 in total) in each of the four arms to complete the trial with 80% power and 2-sided alpha of 1.7%. This will allow three comparisons between arms.

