3.2 Analysis populations

3.2.1 Complete Case Population

All tests of the effect of treatment on outcomes will be conducted on a complete case (CC) population, using intention to treat principles. Patients will be excluded from analyses if they have missing data on any of the variables required for the analysis in question. Those with missing data at baseline will be included in the analysis using the missing indicator method. Detail is given in section 5.3.2. This population will be used for the main analysis of the primary outcome as well as all analyses of secondary outcomes.

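### Filling missing PYY samples with one fitted value that uses randomised arm makes the primary standard errors too small, by an amount that depends on an unstated sample-loss rate

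*SAP*

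**What the plan says.** SAP 5.1 sets the endpoint: "The primary outcome is change in 3-hour time averaged AUC of PYY from baseline to week 24". Each AUC comes from seven samples by the trapezium rule.

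SAP 5.4.1 deals with lost samples. "Those with at least 4 valid values across the sampling time points will be included in the complete case analysis", so up to three of seven may be missing at a visit. For the gaps, "for each time-point a regression model will be fitted that includes BMI, age, ethnicity, randomisation group, and fasting PYY", with fasting PYY left out when the fasting sample is itself the target. Then: "Fitted estimates of PYY will be produced for each participant at each time-point based on the relevant regression model, and used to impute missing data". This is one predicted value per gap, with no random residual and no repetition. The participant's other post-meal samples are not predictors.

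Of the complete case population, SAP 3.2.1 says: "This population will be used for the main analysis of the primary outcome as well as all analyses of secondary outcomes". SAP 5.3.1 regresses the 24-week AUC on arm, and "The effect of the intervention will be adjusted for baseline value of PYY and stratification variables". Nothing there separates a filled AUC from an observed one.

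Two planned analyses bear on this. Multiple imputation (5.4.3) applies only where the whole AUC is missing under the 4-sample rule. The GEE (5.4.2) models the observed 24-week samples with robust standard errors and the same contrasts.

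**The concern.** A fill that includes arm and adds no noise places every filled point exactly on its own arm's fitted line. The points then carry no scatter of their own, so the residual variance falls. They also repeat whatever chance difference exists among the observed samples of that arm, so the true variability of the arm contrast does not fall with it. The primary model sees only the first effect. Its p-values are too small, and they are compared with Holm thresholds (SAP 5.3.2) that presume valid p-values.

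Leaving out the participant's other post-meal samples is a second weakness. It makes the filled AUC less accurate and enlarges the first problem.

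**Working it through.** **The plan's own figure.** SAP 2.3 gives a difference of 120 pg/ml, SD 96.2 pg/ml and "80% power and 2-sided alpha of 1.7" per cent. A noncentral-t calculation gives power 0.768 at 14 per arm and 0.803 at 15, so 15 per arm reproduces; 15/0.8 = 18.75, giving 19 per arm and 76 in total (protocol 11.2). The documents state no error rate for the filled AUC.

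**How much of an AUC can be filled.** With seven equally spaced points the trapezium weights are (0.5, 1, 1, 1, 1, 1, 0.5)/6. The last three carry (1 + 1 + 0.5)/6 = 0.417; three interior points carry 3/6 = 0.50; the fasting point carries 0.5/6 = 0.083.

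**Rough algebra.** Take one time point, n per arm, a fraction f filled, and covariates that predict nothing.
- Fill with arm: each arm mean equals its observed mean, with true variance σ²/(n(1−f)). The model works from about (1−f) of the scatter and counts n people, giving σ²(1−f)/n. Model SE/true SD is therefore about 1−f.
- Fill without arm: gaps take the pooled mean, so the arm difference is multiplied by (1−f). True and model variance both become about 2σ²(1−f)/n, and the ratio is about 1. The error rate is protected, but a real difference is shrunk by (1−f).

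**Simulation under no effect.** From the documents: 4 arms, 15 per arm, 7 samples at baseline and week 24, the 5.4.1 fill, and ANCOVA on arm, baseline AUC and age and BMI strata. Assumed, because the documents are silent: samples lost completely at random, and within-visit correlation 0.5, 0.8 or 0.9. Family-wise error (FWER) is the chance that the smallest of three p-values is below 0.05/3. Each setting had 2,000 to 8,000 replicates (Monte Carlo SE about 0.002 to 0.005).

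| Scattered loss | Correlation | FWER, SAP fill | FWER, complete data | Per-comparison error at 0.017 | Model SE/true SD |
|---|---|---|---|---|---|
| 2% | 0.5 | 0.049 | 0.046 | 0.018 | 0.99 |
| 5% | 0.5 | 0.049 | 0.041 | 0.020 | 0.97 |
| 10% | 0.5 | 0.066 | 0.043 | 0.026 | 0.93 |
| 19% | 0.5 | 0.090 | 0.042 | 0.036 | 0.87 |
| 5% | 0.8 | 0.050 | 0.043 | 0.019 | 0.99 |
| 10% | 0.8 | 0.057 | 0.043 | 0.023 | 0.96 |
| 19% | 0.8 | 0.068 | 0.047 | 0.027 | 0.92 |
| 10% | 0.9 | 0.052 | 0.045 | 0.021 | 0.97 |

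The ratios at correlation 0.5 lie between 1−f (0.98, 0.95, 0.90, 0.81) and 1, as the algebra suggests.

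**Loss in blocks.** With the last three samples lost in 20% to 30% of visits, FWER is 0.069 to 0.075 at correlation 0.5, 0.049 to 0.057 at 0.8 and 0.042 to 0.048 at 0.9. Further runs assumed an adjacent post-meal correlation of 0.92 and a fasting correlation of 0.55 to 0.65. With three samples lost, FWER is 0.066 to 0.074 when 20% of visits are affected and 0.088 to 0.128 when 40% are. With one sample lost in 10% to 20% of visits it is 0.045 to 0.053.

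**Which feature drives it.** The same fill without the arm term, still ignoring the other post-meal samples, kept FWER at 0.038 to 0.050 in every scenario.

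**Alternatives** (last three samples lost in 30% of visits, correlation 0.5):

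| Fill | FWER | Model SE/true SD |
|---|---|---|
| SAP 5.4.1 | 0.075 | 0.92 |
| Arm kept, own other samples added, still fixed | 0.053 | 0.98 |
| Own profile: interpolate, or carry forward at the end | 0.040 | 1.01 |
| Sample-level multiple imputation | 0.036 | 1.03 |

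Other runs with own-profile filling gave 0.036 to 0.047. In runs with an assumed fasting–AUC correlation of 0.56 to 0.59, the RMS error of a filled AUC was 38 to 44 pg/ml under the SAP rule and 13 to 21 pg/ml with own samples.

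**The case against.** The strongest reply is that few samples may be lost. Visits are supervised and the cannula is flushed after each draw (protocol 6.1 and 8.5), so single gaps are at least as plausible as runs of three. That stands: with isolated gaps the inflation is negligible to small, partly because complete-data FWER is already a little under 0.05.

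The fill is also not purely an arm mean. It uses the participant's fasting PYY, BMI, age and ethnicity, and at least half of the AUC weight is always observed. That stands too, and a high within-visit correlation shrinks the problem.

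The SAP is not blind to missing samples either. The GEE would help to expose a result driven by filling. It does not correct the primary p-value, however, and because it adjusts for the baseline fasting value, a disagreement could not be attributed cleanly to the fill.

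Three stronger readings are tempting and unsupported. A reader might infer that ignoring the participant's own post-meal samples is what makes the error bars too small; the fill without arm shows that it is not sufficient alone. A reader might take the 20% dropout in protocol 11.2 as the rate of filled data; a participant with no week-24 samples is excluded under 5.4.1, not filled. A reader might conclude that the primary error rate is known to be badly inflated; no sample-loss rate is given, so only a range that starts near zero can be stated.

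**Conclusion.** The concern holds in direction, with a size that is conditional. The arm term in a fixed, noise-free fill, followed by analysis as if observed, makes the primary standard errors too small. Family-wise error stays at about 0.05 or below with 5% of samples or fewer missing, is about 0.05 to 0.09 at 10% to 20% scattered loss, and about 0.09 to 0.13 if 40% of visits lose three samples, against about 0.04 to 0.05 with complete data. These figures assume loss completely at random; loss related to PYY level was not simulated. The sample size is unaffected. This should be fixed before database lock because the rule permits heavy filling and the remedy is cheap, but it does not by itself invalidate the plan.

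**What to change.** In SAP 5.4.1, remove randomisation group from the fill and use the participant's own samples at that visit:
- for a gap between observed samples, linear interpolation;
- for a missing end sample, the time-point mean pooled over arms plus the participant's mean deviation from the time-point means at the observed samples.

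Dropping arm alone would protect the error rate but pull a real difference towards zero, so both changes belong together. Keep the 4-of-7 rule. Report the number of filled samples by arm and visit, so that readers can see where in the range above the trial falls.

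The cost is a few lines of wording and code, with no new data. The fill remains a single imputation, but simulated error stayed near nominal. Precision hardly changes: in the late-loss run at correlation 0.5, the SD of the estimate was 0.2527 with own-profile filling and 0.2531 with the SAP fill, in the simulation's units. Multiple imputation of single samples, with the other samples as predictors and pooling by Rubin's rules, can be added as a sensitivity analysis.

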5.4.2 Additional Analysis

For a sensitivity analysis, we will also deal with missing data in the primary outcome (PYY postprandial responses at 24 weeks) by running a Generalised Estimating Equations (GEE) model with an exchangeable correlation matrix to compare groups, allowing for repeated postprandial measurements from the same individual. This method allows all individuals with at least a single measure of PYY to be included. In the GEE model with repeated PYY values at 24 weeks as the response variable, the effect of the intervention will be adjusted for the fasting value at the baseline and stratification variables (Age & BMI). Gaussian family distribution with identity link will be used for the response and robust standard errors to provide consistent parameter and standard error estimates. Post-hoc treatment effects for the mean PYY response over the pre to post-prandial assessment period will be analysed according to the same *a priori* contrasts and correction for multiple testing as those reported for the primary analysis.

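### The SAP 5.4.2 sensitivity GEE lists no sampling-time or arm-by-time term while admitting participants with a single PYY sample, so the pattern of missing samples can bias its arm contrasts under stated conditions

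*SAP*

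**What the plan says.** The primary outcome (SAP 5.1) rests on seven samples per visit, one fasting and six at 30-minute intervals after breakfast: "PYY AUC will be derived using the trapezium rule and then divided by time period to calculate the time averaged AUC". For the main analysis, SAP 5.4.1 sets a floor: "Those with at least 4 valid values across the sampling time points will be included in the complete case analysis". Gaps above that floor are filled from a separate regression at each time point.

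SAP 5.4.2 adds a sensitivity analysis on the unsummarised samples, using a "Generalised Estimating Equations (GEE) model with an exchangeable correlation matrix to compare groups". Its scope is wider than the main analysis: "This method allows all individuals with at least a single measure of PYY to be included". The response is each participant's set of individual week-24 PYY values. On the mean model the section says: "the effect of the intervention will be adjusted for the fasting value at the baseline and stratification variables (Age & BMI". Neither sampling time nor an arm-by-time term is named. The reported quantity is the "mean PYY response over the pre to post-prandial assessment period", tested with the same contrasts and multiplicity correction as the primary analysis.

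The summary GEE across weeks 2 to 24 in SAP 5.3.3 is similarly specified, "with an exchangeable correlation matrix adjusted for baseline value and stratification variables (Age & BMI", with no visit term listed.

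**The concern.** PYY is expected to change over the three hours after a meal; that is why it is sampled seven times. A mean model without sampling time gives every sample from a participant the same expected value, so a participant with only a fasting sample enters as an estimate of the whole-window mean. With incomplete profiles, an arm's fitted mean then depends on which samples its members happened to provide.

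The participants whom this analysis adds to the main one are those with one to three week-24 samples, so the omission bears on exactly the cases it is meant to handle. Robust standard errors protect against a wrong working correlation, not against a wrong mean model. At stake is the value of this check: a difference from the primary result could partly reflect the mix of sampling times rather than sensitivity to missing data.

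**Working it through.** **Inputs from the documents.** Target difference 120 pg/ml, SD 96.2 pg/ml, two-sided alpha 1.7%, 80% power, 15 completers per arm (SAP 2.3); 19 per arm after 20% dropout (protocol 11.2). A t-test calculation gives 14.9, so 15 per arm (power 80.3%), and 15/0.8 = 18.75, so 19. The plan's figures reproduce. The unadjusted standard error of one arm contrast is 96.2 × √(2/15) = 35 pg/ml, used below as a yardstick.

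**Assumed, because the documents give no values.** Size and shape of the post-meal rise, within-person correlation ρ, and the pattern of missing samples.

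**Step 1: weights within a profile.** Over 180 minutes in 30-minute steps, the trapezoid average weights the two end samples 15/180 = 1/12 each and the five interior samples 30/180 = 1/6 each. The GEE on a complete profile weights all seven 1/7. An effect that is equal at all six post-meal samples and absent at fasting is multiplied by 6/7 in the GEE and 11/12 in the AUC. The ratio is 0.935, so it is 6.5% smaller even with nothing missing.

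**Step 2: weight of a partial profile.** Under exchangeable correlation a participant with m samples has weight m/(1 + (m − 1)ρ). One sample relative to seven is (1 + 6ρ)/7: 0.40 at ρ = 0.3, 0.57 at 0.5, 0.74 at 0.7 and 0.91 at 0.9.

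**Step 3: hand calculation, no true effect.** Take ρ = 0.7 and a profile of 0, 0.6, 0.9, 1, 0.95, 0.85, 0.75 times a 60 pg/ml peak. The seven-sample mean is 60 × 5.05/7 = 43.3 above fasting. A full profile has weight 7/5.2 = 1.346.
- Two fasting-only beside 15 complete in one arm, none in the other: 2/(15 × 1.346 + 2) = 2/22.19 = 0.090, and 0.090 × (−43.3) = −3.9 pg/ml.
- Four fasting-only: 4/24.19 = 0.165, giving −7.2 pg/ml.
- Milder loss, where the affected participants keep their first three samples: about −1.5 (two) and −2.6 (four).

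**Step 4: simulation of the GEE without a time term.** Two arms, 1,500 per arm, three runs per setting, adjusted for week-0 fasting PYY only, with missingness unrelated to PYY values. Monte Carlo noise is about 1 pg/ml. Entries are the estimated contrast in pg/ml for assumed rises of 50 / 100 / 200 pg/ml.

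| Missing samples | No effect (true 0) | Meal-response effect (true 97.5) |
|---|---|---|
| None | −1.1 / −0.2 / −0.3 | 89.7 / 90.0 / 89.6 |
| 20% fasting-only, both arms | −0.4 / −0.5 / 0.8 | 83.0 / 85.8 / 87.0 |
| 20% fasting-only, active arm only | −4.3 / −5.3 / −6.9 | 80.7 / 81.6 / 81.8 |
| Fasting-only in 1 v 4 of 15 | −5.2 / −6.6 / −8.3 | 78.7 / 76.1 / 79.1 |
| Sampling stops after 30 min, 20% of active arm only | −3.8 / −5.4 / −6.6 | 82.1 / 80.8 / 82.5 |
| Fasting sample missing, 20% of active arm only | 1.0 / 3.5 / 6.0 | 93.2 / 96.2 / 98.4 |

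The balanced row agrees with Step 2. At the fitted ρ of 0.20 (rise 50) the relative weight is (1 + 1.2)/7 = 0.314, the fasting-only share is 0.2 × 0.314/(0.8 + 0.2 × 0.314) = 0.073, and 90 × (1 − 0.073) = 83.4, against 83.0 simulated.

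**Step 5: the same data with time in the model.** A time main effect alone removes the bias when there is no effect (within about 1.4 pg/ml of zero). It gives only 80.6 to 92.9 against 97.5 when the effect varies over the meal. Arm-by-time terms averaged with trapezoid weights give −1.1 to 1.3 against 0, and 96.5 to 98.9 against 97.5.

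**The case against.** **Silence is not exclusion.** The sponsor may intend a time term, and averaging over the assessment period is compatible with one. But the SAP names extra covariates where it wants them (accelerometer wear time, 5.3.3) and models each time point separately in 5.4.1. A programmer following 5.4.2 would fit the listed terms.

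**A plain mean is a legitimate target.** Section 5.4.2 does name a mean over the window. The gap between 90 and 97.5 with complete data is therefore a difference of target, not a missing-data bias. It still means that the check and the primary analysis measure different things.

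**The shifts are small and the patterns chosen.** This largely stands. Participants who miss the week-24 visit contribute no rows, so the 20% dropout allowance does not supply fasting-only cases. Four beside 15 complete would use all 19 in an arm. The null-case hand results of −3.9 and −7.2 pg/ml are about 0.1 and 0.2 of the 35 pg/ml standard error.

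**Stronger readings that do not hold.** A reader might infer that any missing sample biases the contrast; balanced loss with a constant effect does not. A reader might infer that a single-sample participant counts like a full profile; the weight is lower, and depends on ρ. A reader might infer that disagreement with the primary result would be uninterpretable; shifts of this size do not support that, and the multiple imputation in 5.4.3 is a second check without this defect. Finally, a reader might extend the point to the GEE in 5.3.3. That model is for summary purposes, bias would need PYY or the effect to change across visits together with visit-dependent dropout, and no size has been worked out.

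**Conclusion.** The point holds in conditional form. The GEE in 5.4.2, as written, can give a biased arm contrast when the timing of missing samples differs between arms, or when the treatment effect varies over the meal, and then even with balanced missingness. The second condition is plausible for a gut hormone measured after a meal.

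With no true effect, one-sided loss of post-meal samples shifts the contrast by about 4 to 8 pg/ml in the assumed scenarios. With an effect confined to the meal response, 97.5 becomes about 90 through the weighting alone, 83 to 87 with balanced 20% fasting-only participants, and 76 to 79 with 1 versus 4 of 15. The largest loss, 97.5 − 76.1 = 21.4 pg/ml, is about 0.6 of the unadjusted standard error.

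All these sizes rest on assumed meal profiles, correlations and missingness patterns. The primary analysis, the multiple imputation and the sample size are unaffected. The change is worth making before analysis because it costs little, not because the trial's main result depends on it.

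**What to change.** In SAP 5.4.2, add sampling time as a seven-level factor with arm-by-time terms. Report each arm contrast as the average over time points with weights 1/12, five times 1/6, and 1/12, so that it targets the primary outcome. A time main effect alone is not enough when the effect varies over the meal.

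The cost is SAP wording and extra coefficients (6 for time and 3 × 6 = 18 for arm-by-time) in a trial planned for 60 completers. No new data are needed. The change removes the dependence on which times were sampled; it does not address missingness that depends on the PYY values themselves.

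Adding visit and arm-by-visit to the summary GEE in 5.3.3 would be consistent with this. It is optional, and its benefit has not been quantified.

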11. STATISTICS

11.1 Description of Statistical Methods

Participants recruited to the study will be compared within and by treatment group. For the latter, each active treatment arm, whether medication, medication and energy restriction diet or placebo and energy restriction diet, will be compared against the placebo only arm. Baseline variables will be presented by arm using N (%) for categorical variables and mean (standard deviation) or median (interquartile range) as appropriate, for continuous variables.

The primary outcome is change in appetite hormones from baseline to week 24 within and between treatment groups. AUC values for appetite hormone measurements at baseline and 24 weeks will be calculated using the trapezoidal rule. Paired t-tests or equivalent non-parametric tests will be used to analyse the change in appetite hormones within individual treatment groups. One way analysis of variance will be used to calculate mean changes in AUC from baseline to 24 weeks by treatment group. Adjusted treatment effects will be calculated via linear regression analysis or similarly appropriate methods, to compare each treatment against placebo. Models will include a categorical treatment variable and will be adjusted for stratification factors; age and BMI as well as baseline AUC value. Changes in appetite hormones from baseline to weeks 2, 6 and 12 will also be analysed using the same methods; however will represent hypothesis generating analyses only. Similarly, overall changes in appetite hormones over time will be analysed using multilevel models, adjusted for stratification factors.

The analysis for the primary outcome will be repeated for secondary endpoints; changes in resting energy expenditure, weight and body composition, physical activity and biochemical parameters from baseline.

All analyses of outcome data will be carried out on a complete case basis, so only those patients with complete data will be included in the analysis. Intention to treat and per protocol analyses will be carried out as sensitivity analyses, using multiple imputation and including only those who remain on their treatment regimen for the duration of the study, respectively.

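### SAP 5.4.2: the week-24 sensitivity GEE names robust standard errors but no small-sample correction, so as normally run its Holm family error is about 7–8.5% instead of at most 5%

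*SAP*

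**What the plan says.** SAP 5.4.2 plans, as a sensitivity analysis for missing data in the primary outcome, "running a Generalised Estimating Equations (GEE) model with an exchangeable correlation matrix to compare groups". The responses are the repeated PYY values of the week-24 visit, clustered by participant. On the model: "Gaussian family distribution with identity link will be used for the response", with "robust standard errors to provide consistent parameter and standard error estimates". The covariates are the baseline fasting value, age group and BMI group. On who enters: "This method allows all individuals with at least a single measure of PYY to be included". The three contrasts with placebo are then tested with the same "correction for multiple testing as those reported for the primary analysis". SAP 5.3.2 sets those thresholds at 0.017, 0.025 and 0.05.

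SAP 2.3 plans 15 completers per arm, 60 in total. Protocol 11.2 recruits 19 per arm, 76 in total. Neither document names a finite-sample correction or a reference distribution for the GEE.

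**The concern.** The reason given for robust errors is an asymptotic one, and the asymptotics run in the number of participants. The seven blood samples per visit add no independent units. With 60 to 76 participants and seven participant-level parameters (intercept, three arms, baseline, age, BMI), the plain sandwich variance is biased downwards. Referring the statistic to a normal distribution adds a further error in the same direction.

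This analysis exists to show whether the handling of missing data changes the conclusion. If its p-values also move because the variance is understated, a reader cannot separate the two causes, and a borderline contrast may appear to be supported when it is not.

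**Working it through.** **Sample size reproduced.** Inputs from SAP 2.3: difference 120 pg/ml, SD 96.2 pg/ml, two-sided alpha 0.017, power 80%. The normal formula gives 14 per arm. The two-sample t calculation gives 15, with power 80.3%. Dropout: 15/(1 − 0.20) = 18.75, so 19. The participant counts used below are therefore the plan's own. Fifteen per arm is the planned completer number. Nineteen is the upper limit, reached only if everyone has at least one PYY value at week 24.

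**Expected bias by arithmetic.** With complete samples and only participant-level covariates, a Gaussian exchangeable GEE equals least squares on participant means. Its robust variance is then the plain sandwich on those means. Under equal variances and near-balanced arms, that variance is on average about (1 − p/m) of the true one, where m is participants and p parameters. Many implementations multiply it by m/(m − 1). With p = 7:

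- m = 60: (1 − 7/60) × 60/59 = 0.883 × 1.017 = 0.898. The variance is about 10% low and the SE factor is √0.898 = 0.948.
- m = 76: (1 − 7/76) × 76/75 = 0.908 × 1.013 = 0.920. The variance is about 8% low and the SE factor is √0.920 = 0.959.

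**Simulation under no treatment effect.** Four equal arms, adjustment for baseline, age group and BMI group, Holm thresholds 0.017/0.025/0.05. Under the global null the family error is the proportion of trials whose smallest p-value is below 0.017. Assumptions not in the documents: minority strata of 25% (age) and 35% (BMI), and a baseline slope of 0.5. With complete data the slope does not affect the result, because it is fitted. There were 40,000 trials per row, so the simulation error on 8.2% is √(0.082 × 0.918/40,000) = 0.14 percentage points.

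| Variance and reference | 15 per arm | 19 per arm |
|---|---|---|
| Plain sandwich, normal | 8.5% | 7.3% |
| Sandwich × m/(m − 1), normal | 8.2% | 7.1% |
| Sandwich × m/(m − 1), t on m − 7 df | 7.0% | 6.3% |
| Kauermann-Carroll type, t on m − 7 df | 5.2% | 4.9% |
| Mancl-DeRouen type, t on m − 7 df | 3.6% | 3.7% |
| Model-based SE, t on m − 7 df | 4.4% | 4.2% |

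For the second row:

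- The mean robust SE divided by the true SD of the estimate is 0.944 at 15 per arm and 0.953 at 19, in line with the arithmetic above.
- Single-test error at nominal 5% is 7.3% and 6.7%, so interval coverage is about 92.7% and 93.3%.

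**Robustness of the figure.**

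- At 17 per arm the two normal-reference rows give 7.9% and 7.6%.
- At 15 per arm, skewed errors give 7.8% and 7.5%. A placebo-arm SD 1.5 times the others also gives 7.8% and 7.5%.
- A GEE fitted directly to seven time points (4,000 trials per case, m/(m − 1) factor) gives 9.2% and 7.4% with complete data at 15 and 19 per arm, and 8.2% and 7.7% with 10% of values missing at random. The 9.2% carries a simulation error of √(0.092 × 0.908/4,000) = 0.46 points.

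**The case against.** The fairest defence has four parts.

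- The SAP is silent on a correction and does not exclude one. This stands: the figures hold for the usual uncorrected sandwich with a normal reference, which is an assumption about how the SAP will be carried out. But a plan that justifies robust errors by consistency alone should say what it does at 60 participants.
- Robust errors are a sensible choice here, because the exchangeable matrix may be wrong for samples 30 minutes apart. This also stands. Model-based t inference reached 6.8% when the placebo-arm SD was 1.5 times the others. It argues for correcting the sandwich and not for dropping it.
- This is one of several sensitivity analyses. A reader might infer that the trial's alpha is inflated. It is not on this ground: the confirmatory model in SAP 5.3.1 does not specify robust errors. Nor is the GEE planned in a reduced set, since SAP 5.4.4 repeats the primary analysis in the per-protocol set and not this one.
- A reader might infer that the GEE will look more significant than the primary analysis. The documents do not support that. The GEE adjusts for the fasting baseline value, while the primary model adjusts for the baseline value of PYY, which Protocol 11.1 takes as baseline AUC. If AUC correlates 0.6 with its baseline and fasting PYY only 0.4–0.5 (assumed), the GEE's true SE is larger by √(1 − 0.16)/√(1 − 0.36) = 1.15 down to √(1 − 0.25)/√(1 − 0.36) = 1.08. That can outweigh a 4–6% shortfall, so the net direction is not known.

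Two further readings should be resisted. Protocol 11.1 says "overall changes in appetite hormones over time will be analysed using multilevel models, adjusted for stratification factors", which might suggest that the SAP gave up a method with sound small-sample behaviour. The protocol names no REML or degrees-of-freedom method, and it means change across visits, not samples within one visit. Fitted by maximum likelihood with a normal reference, such a model gave 7.6% and 6.9% at 15 and 19 per arm. Second, the across-visit GEE in SAP 5.3.3 also has a formal test, "with significance assigned using the same method as that described for the primary outcome", but that section does not mention robust errors, so the finding does not carry over as written.

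**Conclusion.** The point holds for SAP 5.4.2 alone. Run as a standard sandwich with a normal reference, the week-24 GEE understates its variance by about 8–10% and gives a Holm family error of about 7–8.5% across 15–19 participants per arm. One direct run at 15 per arm reached 9.2%. The comparison with 5% is slightly generous, because with model-based t inference Holm runs at 4.2–4.4% here, the three contrasts sharing one placebo arm. The figures rest on assumed stratum prevalences, an assumed baseline relation and the reading of the SAP's silence as no correction. They change little with skewed errors or unequal arm variances. The consequence is modest but avoidable: a sensitivity result can cross a Holm threshold for a technical reason unrelated to missing data.

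**What to change.** In SAP 5.4.2, keep the GEE and robust errors, and add that the sandwich variance will be small-sample corrected (for example Kauermann-Carroll) and the contrasts referred to a t distribution on participants minus parameters degrees of freedom: 60 − 7 = 53 at 15 per arm, 76 − 7 = 69 at 19. Kauermann-Carroll brings the family error to 5.2% and 4.9%. Mancl-DeRouen is an acceptable but somewhat conservative alternative at 3.6% and 3.7%. If robust errors are also intended for the GEE in SAP 5.3.3, say so there and apply the same correction; otherwise 5.3.3 needs no change on this ground.

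The cost is one sentence, one option in the code and slightly wider intervals. At 15 per arm the widening is about (1/0.948) × (2.006/1.960) = 1.08, and at 19 about (1/0.959) × (1.995/1.960) = 1.06, so roughly 6–8%. No data collection or sample size changes.
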